1 PROTOCOL SUMMARY

1.1 SYNOPSIS

Title:	Randomized Controlled Trial to Evaluate an Implementation Strategy to Increase Optimal Use of HPV Vaccine in Primary Care		
Grant Number:	R01CA2356515-01A1		
Study Description:	We will complete a cluster-randomized trial to evaluate the effectiveness of a multi-component implementation strategy (the intervention) to increase use of the HPV vaccine according to CDC guidelines. Twenty community pediatric practices will be randomly assigned to the intervention or wait-list control condition.		
Objectives*:			
	Primary Objective:	Compare, at 24 months, the proportion of eligible preteens who receive 1st dose (primary endpoint) and 2nd dose (secondary endpoint) of HPV vaccine before their 13th birthday in practices that receive the intervention with practices in the wait-list control group.	
	Secondary Objectives:	Compare these outcomes at 36 months to assess the sustainability of intervention benefit.	
		Determine whether the intervention effect on vaccination outcomes is mediated by providers' increased belief in their capabilities to provide on-time HPV vaccination (primary outcome) and by their increased use of a presumptive, announcement approach to recommend HPV vaccine (secondary outcome)	
		Explore if the intervention effect on vaccination outcomes is mediated by the degree of practice change as measured on an 18-item HPV vaccine delivery score.	
		Assess the implementation fidelity, the acceptability and appropriateness of the intervention for providers, parental satisfaction with care, and cost.	

Endpoints*:	Primary Endpoint: The proportion of eligible preteens who receive the 1st dose of HPV vaccine before their 13th birthday at 24 months post randomization. The proportion of eligible preteens who receive the 2nd dose of HPV vaccine before their 13th birthday at 24 months post randomization.
Secondary Endpoint:	The proportion of eligible preteens who receive the 1st dose of HPV vaccine before their 13th birthday at 36 months post randomization.
	The proportion of eligible preteens who receive the 2nd dose of HPV vaccine before their 13th birthday at 36 months post randomization.
Study Population:	Approximately 120 Community based pediatric primary care providers in the St. Louis metropolitan area , who work in the 20 participating practices
Phase* or Stage:	3 (Low-risk behavioral intervention)
Description of Sites/Facilities Enrolling Participants:	The study will be conducted at Washington University

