For ~15-months, a practice facilitator has worked with 6 practices (20 providers) to implement the intervention, first targeting initiation of HPV vaccine by age 13. All practices were provided with their baseline data and received education about the potential benefit for patients and the practice for following CDC recommendations, a communication strategy, and patient education materials. They identified a QI team and worked with the facilitator towards the practice's goals for improvement. Each practice completed Plan-Do-Study-Act (PDSA) cycles, testing different strategies to improve care. PDSA cycles are small cycles of change that involve reviewing data to assess gaps in performance, identifying possible changes to improve care, selecting and testing an improvement strategy, and monitoring and adjusting new processes for care delivery. To date, the number of team meetings with the facilitator varied from 7 to 11, 10% were by phone, and each visit lasted < 1 hour.

For each provider, HPV initiation was assessed on a randomly selected sample of ~30 patients, 11.0 to 13.0 years old with at least one practice visit (well-child or acute care visit) between June 1st and September 30th in the measurement period. These included 2016, 2017, and 2018. Overall, there was a 19-percentage point increase in HPV vaccine initiation in the 15- months from pre- to post-intervention (62% to 81%), reaching the target for Healthy People 2020.³ Results varied within and across practices as shown in Figure 2.

Efforts to impact vaccine completion by age 13 were initiated in March 2018, and after only 7 months, we observed a 12% increase. The majority (>80%) of providers felt the following features of the intervention were very important in the change process: access to the practice facilitator, the QI practice team, help with measurement and review of vaccination data, and the communication strategy, and all would strongly recommend the program to their colleagues

These findings suggest that the proposed 2-year intervention is feasible and likely to have a large impact and sustained benefits.

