3 OBJECTIVES AND ENDPOINTS

OBJECTIVES	ENDPOINTS	JUSTIFICATION FOR ENDPOINTS	PUTATIVE MECHANISMS OF ACTION
Primary			
To evaluate the effectiveness of the intervention to improve optimal HPV vaccine use.	The proportion of eligible preteens who initiate the HPV vaccine before their 13th birthday, at 24 months. The proportion of eligible preteens who complete the HPV vaccine before their 13th birthday, at 24 months.	Consistent with CDC Guideline Recommendations	
Secondary			
To assess the sustainability of intervention benefit.	The proportion of eligible preteens who initiate the HPV vaccine before their 13th birthday, at 36 months. The proportion of eligible preteens who complete the HPV vaccine before their 13th birthday, at 36 months.		
Tertiary/Exploratory			
To determine whether the intervention effect on vaccination outcomes is mediated by providers' increased belief in their capabilities to provide on-time HPV vaccination (primary outcome) and by their increased use of a presumptive, announcement approach to recommend HPV vaccine (secondary)	The proportion of eligible preteens who initiate the HPV vaccine before their 13th birthday, at 24 months. The proportion of eligible preteens who complete the HPV vaccine before their 13th birthday, at 24 months.		Mediation

OBJECTIVES	ENDPOINTS	JUSTIFICATION FOR ENDPOINTS	PUTATIVE MECHANISMS OF ACTION

To explore if the intervention effect on vaccination outcomes is mediated by the degree of practice change as measured on an 18-item HPV vaccine delivery score.
 
To inform scalability of the intervention, we will assess implementation fidelity, the acceptability and appropriateness of the intervention for providers, parental satisfaction with care, and cost.
	
The proportion of eligible preteens who initiate the HPV vaccine before their 13th birthday, at 24 months.
 
The proportion of eligible preteens who complete the HPV vaccine before their 13th birthday, at 24 months.
 
Implementation fidelity, the acceptability and appropriateness of the intervention for providers, parental satisfaction with care, and cost.
		Mediation

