4.2 SCIENTIFIC RATIONALE FOR STUDY DESIGN

A rigorous evaluation such as the proposed cluster randomized controlled trial is needed to establish the effectiveness of the intervention in a generalizable sample prior to scaling for widespread use. Randomization will be at the level of the practice for two reasons: 1) the intervention is designed to change the system for adolescent vaccine delivery at the practice level, and 2) to prevent contamination of provider behavior within the same practice. The 3-year follow-up required for assessment of sustained change, a key consideration prior to widespread dissemination, precluded a stepped wedge design.

Practices will be recruited from community pediatric practices in the St. Louis metropolitan area and are representative of independent practices where vaccination typically occurs. Our sample size of 20 practices (~80 providers) allows us to test the primary hypothesis and provide interpretable results. All providers (intervention and control groups) will receive information provided by the CDC to assist motivated providers who want to improve use of HPV vaccine that are representative of “usual care.” These will include the current recommendations, background information and the CDC’s patient educational materials and website. The wait-list control group will be offered the intervention after the evaluative study is completed. Initiation of HPV vaccine by age 13 is the primary outcome as local providers suggested this is the most difficult barrier to overcome to achieve optimal use of this effective vaccine. Vaccine outcomes will be assessed at the clinic level using 12-months of routinely collected clinical data to allow for seasonal variation in care delivery patterns (the majority of check-up visits occur in the summer). This measurement approach is characteristic of quality metrics and is needed to show change in vaccine coverage over time, as the guidelines are age-specific. The outcome assessor will be blinded to study group allocation to minimize measurement bias.

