Visit 2 Led by: Practice Facilitator (30-45 mins)	
 ▪ Review baseline HPV vaccination rates for practice/U.S. ▪ Synthesize current HPV vaccination practices, provider individual project goals, and practice goals ▪ Discuss potential opportunities for improvement ▪ Establish practice goals for initiation and completion ▪ Decide focus for initial change idea targeting initiation ▪ Identify resources needed to accommodate change

Month 2	
Visit 3 Led by: Practice Facilitator (30-45 mins) (no more than 2-3 weeks after Visit 2)
 
 ▪ Determine first PDSA cycle to accomplish change idea ▪ Identify process needed to accommodate change ▪ Identify resources needed to accommodate change ▪ Decide how to monitor change
Month 3 – 2 Years	
Subsequent visits during change process Bi-weekly/monthly visits for 2 years (15-45 mins)
 
 ▪ Review success with PDSA cycle(s) and determine next steps ▪ Review considerations to implement change ideas ▪ Determine process for implementing change ideas and PDSA cycles ▪ Support practice QI team and efforts to make changes ▪ Provide education and skills training for providers and staff such as communication strategy, HPV vaccine, parental talking points, etc. ▪ Assist with self-monitoring of HPV vaccination to assess progress ▪ Assist with measurement for PDSA cycles ▪ Provide social support ▪ Share other primary care practices' best practices and change ideas ▪ Provide education for providers and staff about QI methods
Subsequent visits for Maintenance Led by: Practice Facilitator (check in every 2 weeks to monthly for 3 months)	
 ▪ Continue monitoring practice to check for sustainability ▪ Work with practice to trouble shoot any changes or procedures as needed ▪ Make sure the practice has access to all resources and tools as needed ▪ Provide process for obtaining MOC-Part 4 credits

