8 STUDY ASSESSMENTS AND PROCEDURES

8.1 ENDPOINT AND OTHER NON-SAFETY ASSESSMENTS

Mixed methods of data collection will be used including audit of the electronic medical record (EMR) to extract routinely collected and previously recorded data, surveys, and field notes. The study team will follow the same measurement procedures for both study groups.

The primary and secondary outcomes (vaccine initiation and completion by age 13, respectively) will be assessed by audit of the EMR, completed by the research assistant (RA) and/or a member of the study team. To assess variation among providers in the same practice, we will sample records from each participating provider. Measurement will be completed over four 12-month time periods (baseline, 12, 24, and 36 months). For each measurement period, the physician's office will provide an electronic list of eligible patients with an office visit with each participating provider. For each practice, a member of the study team will randomly select a sample of 60 records per provider from this list for review by the RA and or other member of the study team. As much as possible the number of records will be balanced across providers. Data abstracted from the record will include date and type of index visit (well child, acute care, and other e.g., immunization), date of birth, date of vaccination for HPV vaccine, Tdap, and MCV, sex, race/ethnicity and insurance status. Records will be de-identified for patient, provider and practice identifiers, and given a unique subject ID number.

Providers: At baseline and at 12- and 24-months, in addition to the EMR audit described above, all participating providers will complete a brief survey to assess their knowledge, attitudes and behaviors regarding HPV vaccination. The baseline survey will also assess demographic and other practices and physician-level factors that may affect intervention success and are needed to describe the study sample. The practice facilitator will keep detailed field notes about practice observations, contextual factors and practice change components, and will monitor the implementation process.

Practices: At baseline, the project coordinator and/or a member of the study team will meet with the practice manager to complete a brief practice survey to describe the practice and current HPV vaccination procedures. HPV vaccination procedures will be reassessed in a similar manner at 12- and 24- months.

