9.4.2 ANALYSIS OF THE PRIMARY ENDPOINT(S)

Data analyses will adhere to the intention-to-treat principle, allowing 12-months grace period to implement practice changes. The primary analysis will compare the overall proportion of eligible preteens who initiated and completed HPV vaccination in the intervention and control practices at 24 months, using Year 2 measurements for vaccine use. Maintenance of change will be assessed using Year 3 measurements. The analytic approach is to use a multi-level random effects logistic model to account for the hierarchical structure: children clustered within providers clustered within practices.

Define by y_{ijk} as the binary variable of HPV vaccine for the k th child of provider j of practice i . There are 3 hierarchical levels: children clustered within providers clustered within practices. We use random effects to capture the intra-class correlation at the provider and the practice levels. We assume a multi-level random effects logistic model (a generalized linear mixed model):

$$\text{logit } P(y_{ijk}=1) = \beta_0 + trt_{ijk}\beta_1 + a_i + b_{ij} \quad (1)$$

[figure not shown]
where trt_{ijk} is the treatment indicator for practice i , and β_1 is the treatment effect. We use random effects a_i and b_{ij} to describe heterogeneity in the practice level and provider level, and assume $a_i \sim N(0, \sigma_a^2)$ and $b_{ij} \sim N(0, \sigma_b^2)$ are independent. The practice level random intercept is used to accommodate extra-variation in outcome measurements due to clustering of providers in a practice, and the provider level random intercept is used to accommodate extra-variation in outcome measurements due to clustering of individual patients within a provider.

As secondary analysis, we can add other covariates in the model, e.g., gender, category of practice (urban vs. rural), vaccine rate at baseline for a provider or practice, etc. Interaction of treatment and these covariates can be included in the model to study the moderating effect of these risk factors. The interaction of random effects (both at the practice and provider levels) and covariates can be added in the model as well.

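### Second-dose completion at 24 months is labelled primary in some sections and secondary in others, with no rule for the case where it and initiation disagree; reconcile the labels to initiation as sole primary

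*Combined protocol and SAP*

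**What the plan says.** The current text of the combined protocol and SAP gives 24-month completion three different standings.

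- **Secondary.** The synopsis objective compares the proportions who "receive 1st dose (primary endpoint) and 2nd dose (secondary endpoint) of HPV vaccine before their 13th birthday". Section 8.1 agrees: "The primary and secondary outcomes (vaccine initiation and completion by age 13, respectively".
- **Primary.** The synopsis endpoint list, under its Primary Endpoint label, includes "The proportion of eligible preteens who receive the 2nd dose of HPV vaccine before their 13th birthday at 24 months post randomization". The Primary row of the Section 3 table includes "The proportion of eligible preteens who complete the HPV vaccine before their 13th birthday, at 24 months".
- **Part of the primary analysis.** Sections 9.3 and 9.4.2 share one sentence: "The primary analysis will compare the overall proportion of eligible preteens who initiated and completed HPV vaccination".

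Other sections name initiation alone. Section 4.2 says "Initiation of HPV vaccine by age 13 is the primary outcome" and gives a reason. Section 9.2 bases the sample size on initiation, with 0.40 against 0.53.

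Two places leave the dose open. The hypothesis in 9.1 speaks of receiving HPV vaccine without saying which dose, and y in model (1) of 9.4.2 is defined in the same general way.

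Section 9.4.1 sets two-tailed P < 0.05 for all main analyses. The only multiplicity adjustment is the Bonferroni correction for the Aim 2 mediation tests in 9.2. Section 9.4.3, on secondary endpoints, covers mediation and implementation outcomes and contains no between-arm comparison of completion.

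**The concern.** A reader who starts from Section 8.1 and one who starts from the synopsis endpoint list can judge the same results differently. Suppose initiation is significant and completion is not. The trial is positive if initiation is the only primary endpoint, and negative if both are required. In the reverse case it is negative under both of those rules, and positive only if either outcome suffices.

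Disagreement between the two outcomes is a practical possibility, because completion is targeted in its own right. Table 2 in Section 6.1.2 has each practice "Establish practice goals for initiation and completion", and Section 2.2 reports for the pilot: "Efforts to impact vaccine completion by age 13 were initiated in March 2018, and after only 7 months, we observed a 12% increase".

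The interpretation of the headline result is at stake, not the data collection or the model. Section 6.3 blinds the data analyst to group assignment, which limits the room to choose a reading after the fact. It does not remove it, because the same section says that the investigators cannot be blinded.

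**Working it through.** **1. The passages side by side**

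| Place | Standing of 24-month completion |
|---|---|
| Synopsis, primary objective | secondary |
| Synopsis, endpoint list | primary |
| Section 3, Primary row | primary |
| Section 4.2 | not named; initiation is the primary outcome |
| Section 8.1 | secondary |
| Section 9.1 | dose not specified |
| Section 9.2 | not powered; initiation is the primary outcome |
| Sections 9.3 and 9.4.2 | inside the primary analysis, with initiation |
| Model (1), definition of y | dose not specified |
| Section 9.4.3 | no comparison given |

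Broken table layout does not explain the conflict. The synopsis and Section 3 both list the 36-month outcomes separately as secondary, and 9.3 and 9.4.2 are running text.

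**2. The plan's power figure, which is for initiation**

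Inputs from Section 9.2: 10 practices per arm, 4 providers per practice, 30 children per provider, practice variance 0.01, provider variance 0.75² = 0.5625, rates 0.40 and 0.53. I read the rates as population averages.

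Variance of the log-odds in one arm = [0.01 + (0.5625 + 1/(30·I))/4]/10, where I is the mean of p(1−p) over providers.

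- Control: I = 0.2139, variance 0.01896.
- Intervention: I = 0.2213, variance 0.01883.
- Log-odds difference: 0.592. SE = √(0.01896 + 0.01883) = 0.1944.
- Power = Φ(0.592/0.1944 − 1.960) = Φ(1.087) = 0.86.

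Fitting model (1) to 400 simulated trials gave 0.855. Both agree with the stated power of over 0.80. If the rates are instead those of a provider with zero random effect, power is about 0.77. In either case the figure concerns initiation only. The documents give no expected completion rate, so power for completion cannot be derived from them.

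**3. What each reading implies**

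- *Initiation alone is primary.* Error is 5% and power is as in step 2.
- *Both required.* Error is at most 5%. Power depends on completion rates that are not stated. For illustration only, if each outcome had an assumed 80% power, joint power would be 0.80² = 0.64 with independent tests and 0.73 at a test correlation of 0.8.
- *Either suffices, each at 0.05.* Error exceeds 5%. With independent tests it would be 1 − 0.95² = 0.0975. The tests are not independent, because only a child who has initiated can complete.

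**4. Size of the either-suffices error**

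I simulated the no-effect case with 10 practices per arm, 4 providers per practice, 60 records per provider (the amended number), the 9.2 variances and initiation 0.40 in both arms. Two inputs are assumed: the mean share q of initiators who complete, and the between-provider SD s of that share on the logit scale. The test was a t-test on practice means with 18 df, standing in for model (1). There were 20,000 runs per row.

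| q | s | Correlation of tests | Either significant |
|---|---|---|---|
| 0.30 | 0.75 | 0.57 | 8.7% |
| 0.30 | 0 | 0.81 | 7.9% |
| 0.50 | 0.75 | 0.72 | 8.2% |
| 0.50 | 0 | 0.90 | 7.1% |
| 0.65 | 0.75 | 0.82 | 7.7% |
| 0.65 | 0 | 0.94 | 6.7% |
| 0.85 | 0.75 | 0.95 | 6.8% |
| 0.85 | 0 | 0.98 | 6.0% |

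Initiation alone stayed at 5.0-5.2%. As a check, the bivariate normal formula gives 8.8% at correlation 0.58 and 5.9% at 0.98. About half of the error in each row falls in the intervention's favour (2.9-4.4%, against a nominal 2.5%).

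**The case against.** The strongest reply is that the intent is already clear. Four explicit statements (synopsis objective, 4.2, 8.1, 9.2) agree, two of them label each outcome by name, and the only numerical contrast belongs to initiation. This stands, and it is why the labels should be reconciled to initiation. It does not make the text consistent: the endpoint list and the Section 3 Primary row still say otherwise, and no decision rule overrides them.

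A second reply is that placement proves little here. Section 9.4.2 also holds the 36-month analysis, which is secondary elsewhere, and 9.4.3 holds mediation, which Section 3 places in its tertiary rows. The Section 3 table groups endpoints by objective and repeats 24-month completion in those tertiary rows. This also stands. Appearing in 9.4.2 or in the Primary row is weaker evidence of rank than an explicit label, and the clearest conflict is the one inside the synopsis.

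Two stronger readings are tempting. One is that the trial has no identifiable primary outcome. The four statements above contradict that. The other is that the plan runs at an inflated error of 6-9%. That would follow only from an either-suffices rule, which the plan does not adopt. What can be said is that the plan does not exclude it.

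**Conclusion.** The plan is wrong as written on this point, and the repair is small. The status of 24-month completion is contradictory in current text, and nothing says how the trial is judged if initiation and completion disagree. That conclusion needs no assumptions.

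The size is conditional. The two-sided error would be about 6-9% under an either-suffices rule, given an assumed 30-85% completion among initiators, an assumed provider-level spread in that share, and a practice-mean test in place of model (1). It is 5% if initiation alone is primary, and at most 5% if both are required. The stated power for initiation is not in question here. Power for completion, and so for a both-required rule, cannot be judged from the documents.

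**What to change.** Before any 24-month comparison by arm:

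- Name initiation before the 13th birthday at 24 months as the sole primary endpoint, tested at two-sided 0.05.
- Label 24-month completion secondary in the synopsis endpoint list, Section 3, 9.3 and 9.4.2.
- Specify initiation in the 9.1 hypothesis.
- In 9.4.2, define y in model (1) as initiation for the primary analysis.
- In 9.4.3, state that the same model is applied to completion as a secondary analysis.

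The 36-month outcomes stay secondary.

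The cost is wording in six places (synopsis, Section 3, 9.1, 9.3, 9.4.2, 9.4.3). Sample size, data collection and power for initiation do not change. The downside is that completion carries no confirmatory claim. If the investigators want one, completion can be tested at 0.05 only after initiation is significant. That step is optional: it would keep the overall error at 5%, but completion could then be claimed only in a trial where initiation succeeds.
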